
Follow-up visit (Day 15) 1.5-2 hours
	
 • Complete in-person Caffeine Withdrawal Symptoms Questionnaire (CWSQ, parent and child together) • Dietary recall (parent and child together) • Beverage taste testing (child participant) • Return empty study beverages • Qualitative interview (~20 minutes, parent and child together)

Details of all study procedures are described below:

Study Procedure	Description
Height and weight	Child participant's height and weight will be measured using a portable scale and stadiometer.
Caffeine Withdrawal Symptoms Questionnaire (CWSQ)	Parent and child participants will together complete a child-adapted version of the validated CWSQ ⁸ in person at baseline, and online daily throughout the intervention. [name] and/or a trained RA will assist with CWSQ completion at baseline and will counsel participants regarding filling out the online questionnaire.
24 hour dietary recalls	Participants will be asked (with the help of their parent) to report everything that they eat and drink over the past 24 hours. 24-hour recalls will be conducted at baseline (in person), after 1 week of the intervention (in person or via phone depending on participant preference), and at follow-up (in person).
Beverage taste testing	Prior to randomization, child participants will taste pairs each study beverage (10 mL) in randomized order and rate which beverage they like better and which beverage tastes sweeter using the taste enclosed taste testing form. Participants will rinse with water between each test. Taste testing will be completed in a private room and supervised by trained RAs. Child participants will also complete taste testing at follow-up.
Compliance questionnaires	Participants (child and their parent) will complete an online, 4-item questionnaire daily throughout the intervention to assess compliance (percentage of assigned beverages consumed, assessment of whether caffeinated SSB were consumed in violation of the study protocol, and if so, the brand and quantity consumed).
Randomization and Blinding	Following baseline assessments, child participants will be randomized using sex-stratified permuted block randomization into one of three arms: 1) caffeine-free SSBs (caffeine-free Pepsi) 2) unsweetened sparkling water (LaCroix) or 3) control (Pepsi).

	Assigned beverages will replace usual caffeinated SSB consumption, as assessed at enrollment.

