Beverage distribution	A two-week supply of beverages (corresponding to randomization and the amount of SSBs typically consumed) will be provided. If a participant runs out of beverages, the study team will provide additional beverages. Children will be counseled to drink only the study drinks provided or water and not to consume any other beverages during the two week intervention. Parents will also be counseled regarding encouraging their child to consume only the study beverages or water throughout the two week study period.
Compliance and reminders	Compliance will be assessed by collection of empty beverage containers. Empty containers will be picked up by the study team at the end of the intervention to minimize participant burden. If a participant is provided with additional beverages, empty containers will be requested prior to distribution of more beverages. Compliance will be further monitored during dietary recalls.
Mitigation of withdrawal symptoms	If a child experiences headaches, nausea, or other discomfort, they will be asked to report symptoms using the CWSQ before taking pain or anti-nausea remedies. Children and their parents will be discouraged from using over-the-counter medications, unless the severity of the symptoms are reported to be above a pre-determined threshold (rating of 4 or higher on the CWSQ Likert scale). In addition, participants will be strictly instructed not to use any pain remedy containing caffeine.

Data analysis:

Caffeine withdrawal scores will be collected using the CWSQ, completed by the child and parent together. Peak withdrawal symptoms will be operationalized as CWSQ scores reported within the initial 72 hours of the intervention, between the three groups. Univariate analyses and one-way ANOVA will be used to assess group differences in our primary (measures of compliance with beverage intervention) and secondary (withdrawal symptoms) study outcomes.

Dietary recalls will allow us to assess adherence to the study beverages as replacements for habitual caffeinated SSBs and to determine if caffeinated SSB removal impacts dietary choices. While we acknowledge limitations inherent to self-report dietary assessment, dietary recalls are sufficient for capturing beverage consumption data and will enable us to determine whether participants change their diet to compensate for caffeine restriction.

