Compliance with beverage consumption will be assessed using beverage/compliance logs (completed by the parent and child together). We will operationalize compliance as the number of days in which participants consumed the study beverages, the total number of study beverages consumed during the intervention period, as well as any consumption of caffeinated SSB, juices etc. (in violation of the study protocol). Importantly, participants are being instructed simply to consume the study beverages in the same manner that they would normally consume their usual caffeinated sugar-sweetened beverages. They will not be assigned to consume a certain number of study beverages, but instead instructed to replace their usual beverages with the study drinks or water throughout the intervention period.

Liking of study drinks may affect compliance and we will therefore run exploratory multivariable linear regression models including taste ratings as a potential confounder, along other potential covariates such as sex, race/ethnicity, age, weight, and volume of habitual SSB consumption. While we recognize that we are not sufficiently powered for multivariable regression models including a large number of covariates, these data will be critical in informing sample size calculations for our subsequent R01 proposal. We will use an intention to treat (ITT) approach and will minimize loss to follow-up by maintaining close contact with participants. All analyses will be conducted using SAS 9.4.

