Official Title: Investigating Withdrawal Symptoms as Barriers to Reducing Sugar-sweetened Beverage Consumption among Children

NCT #: Not yet assigned

Date: July 15th, 2019

Statistical Design and Power

The primary purpose is to evaluate primary the feasibility of the intervention and therefore, formal sample size calculations for clinical outcomes were not performed. We will enroll a total of 60 participants (n=20 per group).

This study includes an intervention to remove caffeinated SSBs and to explore whether caffeinated SSB removal induces withdrawal symptoms in 8-11 year old (3rd-5th grade) children. Child participants in the clinical pilot study will be randomly assigned to replace their usual caffeinated SSB consumption with either caffeinated SSBs provided by the study team, caffeine-free SSBs or unsweetened sparkling water (also provided by the study team) for two weeks.

Caffeine withdrawal scores will be collected using caffeine withdrawal symptom questionnaires (CWSQ, completed by the child and parent together). Peak withdrawal symptoms will be operationalized as CWSQ scores reported within the initial 72 hours of the intervention, between the three groups. Univariate analyses and one-way ANOVA will be used to assess group differences in our primary (measures of compliance with beverage intervention) and secondary (withdrawal symptoms) study outcomes.

Compliance with beverage consumption will be assessed using beverage/compliance logs (completed by the parent and child together). We will operationalize compliance as the number of days in which participants consumed the study beverages, the total number of study beverages consumed during the intervention period, as well as any consumption of caffeinated SSB, juices etc. (in violation of the study protocol). Importantly, participants are being instructed simply to consume the study beverages in the same manner that they would normally consume their usual caffeinated sugar-sweetened beverages. They will not be assigned to consume a certain number of study beverages, simply to replace their usual beverages with the study drinks and to consume only the study drinks and water throughout the intervention period.

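### The primary compliance outcome is a percentage with no defined denominator in the procedures but raw counts in the analysis, and the raw total mixes usual intake with uptake of the study drink

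*Protocol*

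**What the plan says.** Compliance is the primary outcome in both documents, and arms are to be compared by univariate analyses and one-way ANOVA.

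- **Protocol, section D, procedures table, Compliance questionnaires row:** the daily four-item form assesses the "percentage of assigned beverages consumed", together with any caffeinated SSB drunk against the rules.
- **Protocol, section D, Data analysis:** "We will operationalize compliance as the number of days in which participants consumed the study beverages", then "the total number of study beverages consumed during the intervention period, as well as any consumption of caffeinated SSB, juices etc". No percentage appears. The same paragraph states: "They will not be assigned to consume a certain number of study beverages". Children are "instructed to replace their usual beverages with the study drinks or water throughout the intervention period".
- **SAP, Statistical Design and Power:** the same three measures, including "the total number of study beverages consumed during the intervention period", again without a percentage.
- **Protocol, procedures table, Beverage distribution row:** "A two-week supply of beverages (corresponding to randomization and the amount of SSBs typically consumed) will be provided". Then: "If a participant runs out of beverages, the study team will provide additional beverages".
- **Protocol, Appendix, Compliance Questionnaire:** yes/no and a quantity in cans or ounces. It has no target amount.
- **Protocol, section E:** entry requires at least 12 oz of caffeinated SSB a day. No upper limit is given.

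Habitual SSB volume enters the analysis only as a possible covariate in exploratory regressions, which both documents describe as underpowered.

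**The concern.** There are two linked problems.

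First, the procedures and the analysis describe the primary outcome differently, and the percentage cannot be computed from the daily form as described. An analyst who tried would have to choose between initial supply, total supply after restocking, and usual intake at enrolment. These choices give different answers for the same child.

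Second, deleting the percentage leaves the raw total. Supply is matched to usual intake and usual intake has no ceiling, so the total partly records how much soda a child drank before the study. Randomisation is stratified by sex only and the ANOVA is unadjusted. With 20 children per arm, variation in usual intake becomes noise in the arm comparison and chance imbalance goes uncorrected. That comparison is the test of the Protocol's hypothesis that compliance is lowest with sparkling water.

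**Working it through.** The plan states no figure on this point, so there is nothing to reproduce.

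**Inputs from the documents:** 14 intervention days; entry at 12 oz/day or more; 12 fl oz = one can (Beverage Questionnaire band label); 20 children per arm.

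**1. Restocking moves the denominator.** A 12 oz/day child is supplied 12 × 14 / 12 = 14 cans, drinks 21, and receives 14 more.
- Initial supply: 21 / 14 = 150%.
- All cans supplied: 21 / (14 + 14) = 75%.

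**2. The measures can reverse two children.** Uptake = study-drink ounces / (days × usual ounces per day).

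| Child | Usual oz/day | Cans drunk | Uptake | Days |
|---|---|---|---|---|
| Light user, replaces all | 12 | 14 | 168 / 168 = 100% | 14 |
| Heavy user, replaces half | 36 | 21 | 252 / 504 = 50% | 14 |

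The total favours the heavy user, uptake favours the light user, and days can tie them. If every child had the same usual intake and no restocking occurred, the percentage would be the total divided by a constant and the orders would be identical.

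**3. Size under assumptions that are not in the documents.** Usual intake is lognormal, median 16 or 24 oz/day, log-SD 0.3 or 0.5, limited to 12–60 oz. The mean fraction replaced is 0.9, 0.9 and 0.7 by arm, SD 0.2. There are 60 children per simulated trial, and alpha is assumed to be 0.05. Discordance = (1 − Kendall tau) / 2.
- Total and uptake order 23% to 31% of pairs oppositely. A second model (usual intake of 1, 2 or 3 cans a day in several mixes, replacement drawn from beta distributions) gave 10% to 30%.
- Power of the three-arm test is about 0.4 to 0.6 on the raw total and about 0.9 on the uptake ratio, if usual intake is known exactly.

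**4. Error in reported usual intake.** Multiplying reported usual intake by lognormal error and repeating step 3 gives approximate power as follows:

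| Error (log-SD) | Raw total, ANOVA | Uptake ratio, ANOVA | Total adjusted for usual intake, ANCOVA |
|---|---|---|---|
| 0 | 0.4–0.6 | 0.9 | 0.8–0.9 |
| 0.3 | 0.4–0.6 | 0.5 | 0.5–0.7 |
| 0.5 | 0.4–0.6 | 0.2 | 0.4–0.6 |

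At 0.3 the ratio loses most or all of its gain. At 0.5 it is worse than the raw total. ANCOVA did as well as or better than the raw total in every setting.

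**The case against.** The strongest reply is that the operative definitions do not conflict. The Protocol's analysis text and the later SAP give the same three measures, and the percentage is a parenthesis in a procedures table. On the wording alone this stands: deleting the phrase would remove the contradiction. It would not change what the raw total measures.

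Three further points stand and limit the finding.

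- **Other measures are planned.** The total is one of three. If the heavy user in the example fills the gap with other soda, the off-protocol measure should record it. If the gap is filled with water, the child has followed the instruction. A child who replaces everything with water has 0% uptake and no violation, so an uptake percentage is not a replacement percentage.
- **The trial compares arms and does not rank children.** Under the step 3 assumptions the sparkling-water arm still had the lowest mean total in about nine trials in ten or more.
- **The ratio has its own weaknesses.** It can exceed 100%, it depends on which days are reported, and its denominator comes from a banded form.

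A reader might infer that no denominator exists, or that heavy users will necessarily look like the best compliers. The documents support neither. Supply is matched to usual intake, and the Randomization row refers to consumption assessed at enrolment, so candidate denominators exist but none is named. Whether rankings reverse depends on the spread of usual intake, which is not given. Nor is the arm comparison shown to be biased: randomisation balances usual intake on average, so the cost is precision and chance imbalance.

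**Conclusion.** The point holds in a limited form. The primary outcome is described in two ways, and the percentage has no defined denominator. The unadjusted raw total mixes usual intake with uptake and can order two children wrongly as a measure of uptake. The wording conflict, the 150%/75% example and the 14-versus-21-can example need no assumption beyond a 12 oz can and the illustrative intakes.

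The size does rest on assumptions. About 10% to 31% of pairs are ordered oppositely across the two models. The power gain from accounting for usual intake is large if it is measured well and small or absent if it is measured badly. This should be settled before analysis; it is no reason to hold up the pilot.

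**What to change.** 1. Use one definition in the Protocol's procedures table, the Protocol's analysis text and the SAP. Either delete the percentage or define it as study-drink uptake = study-drink ounces / (days reported × usual caffeinated-SSB ounces per day at enrolment).
2. If it is kept, state that supplied or restocked cans are not the denominator, and how values above 100% and unreported days are handled. State also which Beverage Questionnaire rows count (for example, whether sweet tea does) and what value each band takes, including the open-ended and overlapping ones such as 2+ and 3+ times a day.
3. Convert cans to ounces. In the main arm comparison of total study drinks, adjust for usual caffeinated-SSB volume at enrolment by ANCOVA rather than leaving it to the exploratory models. Report the uptake percentage beside it.
4. Call the measure uptake, not replacement, because water is allowed, and always read it with the off-protocol measure.

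The cost is wording in three places, one derived variable and one covariate, with no new data if the appended Beverage Questionnaire is the enrolment source. The drawback is that usual volume from a banded form carries error, which harms the ratio more than the covariate adjustment.

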- a. Male
- b. Female

2. How old is your child? _____ years

3. What is your child's race?

- a. White/Caucasian
- b. Black/African American
- c. Asian
- d. Mixed race
- e. Other, please specify _____
- f. Prefer not to answer

4. Is your child Hispanic?

- a. Yes
- b. No

5. Is your child eligible for free or reduced-price lunch?

- a. Yes
- b. No

6. Were you born in the United States?

- a. Yes
- b. No

If no, where were you born? _____

When did you move to the United States? _____

7. Was your child born in the United States?

- a. Yes
- b. No

If no, where was your child born? _____

When did you move to the United States? _____

Compliance Questionnaire

1. Did you drink the assigned study beverages {insert specific type for participant per randomization} today? If so, how many?

Please circle: YES or NO

Quantity: _____ cans OR _____ ounces

Brand and name of beverage:

2. Did you drink any other sugar beverages today? If so, which ones and how many/how much?

Please circle: YES or NO

Quantity: _____ cans OR _____ ounces

Brand and name of beverage:

3. Did you drink juice today? If so, what kind and how much?

Please circle: YES or NO

Quantity: _____ cans OR _____ ounces

Brand and name of beverage:

4. Did you have any caffeinated beverages, such as coffee, tea, or hot chocolate today? If so, which ones and how many/how much?

Please circle: YES or NO

Quantity: _____ cans OR _____ ounces

Brand and name of beverage:

Beverage Questionnaire

Name: _____

Date: _____

Instructions

In the past month, please indicate your response for each beverage type by marking an "X" in the square for "how often" and "how much each time".

1. Indicate how often you drank the following beverages, for example, if you drank 5 glasses of water per week, mark 4-8 times per week.
2. Indicate the approximate amount of beverage you drank each time, for example, if you drank 1 cup of water each time, mark 1 cup under "how much each time".
3. Do not count beverages used in cooking or other preparations, such as milk in cereal.
4. Count milk added to tea and coffee in the tea/coffee with cream beverage category NOT in the milk categories

Type of Beverage/Drink	HOW OFTEN (MARK ONE)							HOW MUCH EACH TIME (MARK ONE)				

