Low Fat/Fat Free Milk (Skim, 1%, Buttermilk, Soy milk)												
Regular, caffeinated, Soft Drinks/ Regular Soda with caffeine (e.g. Coke, Pepsi, Mountain Dew)												
Caffeine-free Regular Soft Drinks/Soda (e.g. Sprite, Fanta, Caffeine-free Coke)												
Diet/Artificially Sweetened Soft Drinks including diet soda, (e.g. Diet Coke, Diet Pepsi, Coke Zero)												
Caffeine-free Artificially Sweetened Soft Drinks/Soda (e.g. Caffeine-free Diet Pepsi, Diet Sierra Mist, Sprite Zero)												
Sweet Tea (e.g. Arizona Iced Tea, Nestea, Pure Leaf)												

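### The daily compliance form has no item for caffeine-free diet drinks or plain milk, so the log-based violation measure can miss breaches of the study-drinks-or-water rule

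*Protocol*

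**What the plan says.** **The rule.** In the Protocol (section D, study procedures table, Beverage distribution) children are told to keep to study drinks or water and "not to consume any other beverages during the two week intervention". The SAP (Statistical Design and Power) has them "to consume only the study drinks and water throughout the intervention period". Neither document makes an exception for any arm.

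**The daily form.** The Compliance questionnaires row of the same table says that the form has four items. The appendix prints them:

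- Item 1: "Did you drink the assigned study beverages", with quantity.
- Item 2: "Did you drink any other sugar beverages today? If so, which ones and how many/how much".
- Item 3: juice.
- Item 4: caffeinated beverages, with coffee, tea and hot chocolate as examples.

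There is no open item for anything else.

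**The outcome.** Compliance is the primary outcome. The Protocol (Data analysis) and the SAP assess it from the logs by three measures: days on which study beverages were drunk, total study beverages drunk, and violations, worded "as well as any consumption of caffeinated SSB, juices etc. (in violation of the study protocol".

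**Other sources.** The 24-hour recalls cover all food and drink and are also named as a compliance source. They take place at baseline, after week 1 and at the Day 15 follow-up. The appendix Beverage Questionnaire, which measures habitual intake, gives separate rows to drinks that the daily form omits, for example "Caffeine-free Artificially Sweetened Soft Drinks/Soda".

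**The concern.** The rule is wider than the form that monitors it. A child could drink caffeine-free diet soda or plain milk every day, break the rule as written, and truthfully answer no to items 2, 3 and 4. That child's log would show no violation.

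Compliance is the primary outcome, and the pilot is meant to inform a larger trial. Aim 1 predicts the lowest compliance with sparkling water, the only arm without a sweet drink. If children there turn to sugar-free sweet drinks more often than children in the two cola arms, the violation measure loses part of the contrast that Aim 1 looks for. Daily data that were never asked for cannot be recovered afterwards.

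**Working it through.** The plan states no figure on this point, so there is none to reproduce. The check has three steps.

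**1. Coverage of the daily items.** The Beverage Questionnaire has 20 rows, 19 without water. Each row is matched to the first of items 2 to 4 that would record it.

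| Daily item | Rows matched | Number |
|---|---|---|
| 2, other sugar beverages | sweetened juice drinks, caffeinated regular soda, caffeine-free regular soda, sweet tea, energy drinks, sports drinks | 6 |
| 3, juice | 100% fruit juice | 1 |
| 4, caffeinated beverages | diet soda, diet iced tea, three hot tea or coffee rows, diet energy drinks | 6 |
| None | diet fruit drinks, whole milk, 2% milk, low-fat milk, caffeine-free diet soda, diet sports drinks | 6 |

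Unmatched: 6/19 = 32%. If families report light juice drinks under juice, it is 5/19 = 26%. Leaving out the three milk rows, the unmatched sugar-free sweet drinks are 3/19 = 16%. These are shares of categories, not of consumption.

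**2. What the recalls can recover.** The baseline recall precedes the intervention, which leaves two recalls for 14 days: 2/14 = 14%. Suppose a child takes an unasked drink on k of the 14 days, the two recall days are effectively random relative to those days, and reporting is complete. Then

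P(seen at least once) = 1 − C(14−k, 2)/C(14, 2), with C(14, 2) = 91.

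For k = 3 this is 1 − 55/91 = 0.396. The last column is k/14, which applies if only the mid-point recall falls inside the window.

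| Days with an unasked drink (k) | Seen, two recalls | Seen, one recall |
|---|---|---|
| 1 | 14% | 7% |
| 2 | 27% | 14% |
| 3 | 40% | 21% |
| 5 | 60% | 36% |
| 7 | 77% | 50% |
| 10 | 93% | 71% |
| 14 | 100% | 100% |

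The recalls find habitual users and miss most occasional ones. They do not give a 14-day count for anyone.

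**3. Illustration of the effect on the Aim 1 contrast.** All rates here are assumptions. Compare the share of children with any violation in two arms of 20, at two-sided alpha 0.05, using the normal approximation

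power = Φ{[(p1 − p2) − 1.96 √(2p̄(1 − p̄)/n)] / √([p1(1 − p1) + p2(1 − p2)]/n)}.

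Take a true share of 60% with sparkling water and 30% in control, and let some sparkling-water children violate only with unasked drinks (none in control). With nothing hidden, p̄ = 0.45 and power = Φ[(0.300 − 0.308)/0.150] = 0.48.

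| Hidden in sparkling-water arm | Apparent adherence (true 40%) | Power |
|---|---|---|
| 0 points | 40% | 48% |
| 10 points | 50% | 25% |
| 20 points | 60% | 10% |
| 30 points | 70% | 2.5% |

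In the last row the apparent shares are equal, so 2.5% is only the chance of a false positive in the predicted direction. With a true share of 50% in the sparkling-water arm, power falls from 25% to 2.5% when 20 points are hidden; with 70%, it falls from 73% to 25%.

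**The case against.** A reader might infer that sparkling-water compliance is overstated, that the predicted difference is hidden, and that feasibility is overstated. The documents do not support any of these as a finding, for four reasons.

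- **Only one of three measures can be inflated.** Days with study beverage and total study beverages come from item 1. A child who swaps sparkling water for diet soda would leave these flat or lower. This stands. It does not close the gap, because no quantity is assigned and water is allowed, so a low count cannot be read as a breach.
- **These drinks may not be meant to count.** Aim 1 is about removing caffeinated SSBs, the Compliance questionnaires row describes the form as detecting caffeinated SSBs, and the limitations paragraph worries about products with caffeine or sugar. A child who drinks caffeine-free diet soda is still avoiding caffeinated SSBs, so overstated feasibility does not follow. This stands too. It also shows that the documents do not agree on what a violation is, since the violation measure ends in an open-ended etc. while the drinks rule bars everything else.
- **Other sources partly cover the gap.** The recalls ask about all drinks, and a child who takes such a drink every day would show it on both on-treatment recalls. The debrief asks how hard it was to keep to the study drinks and whether the child got other beverages elsewhere. So the drinks go unasked on the daily form only. The debrief is a single qualitative interview, and the recalls miss most occasional use.
- **A bias specific to one arm is an inference.** The gap exists in all three arms, half of the unmatched categories are milk, and no substitution rate is given.

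**Conclusion.** The point holds as a gap between rule and form. Both documents bar every drink except study drinks and water, and the daily form cannot record 6 of 19 non-water categories. The log-based violation measure can therefore miss breaches of the stated rule, and the recalls fill in only about 2 of 14 days. Adherence on that measure may be overstated, by an amount that the documents do not let one estimate.

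Blunting of the Aim 1 contrast depends on sugar-free substitution being commoner with sparkling water. That is plausible, but the power figures above rest on assumed rates and show only what could happen. The finding is minor and is worth acting on because the remedy is cheap and the data cannot be collected later.

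**What to change.** - Add one daily item, for example: *Did you drink anything else today apart from water, such as milk or diet or sugar-free drinks? Which, and how much?* This raises coverage from about 2 to all 14 days.
- Change the item count in the Compliance questionnaires row from four to five.
- Report these drinks by arm as their own category, separate from caffeinated SSBs, other sugar drinks and juice.
- Reconcile the Compliance questionnaires and Beverage distribution rows, the Protocol's Data analysis text, the appendix form and the SAP on which drinks count as a violation, and replace the open-ended etc. with a list. This point takes no position on which drinks should be allowed.

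The cost is one more short question per day for each family, one REDCap field, and a small edit to both documents.
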